In toxicology studies completed to date, no notable adverse events were identified after 2 weeks of topical ocular dosing. Likewise, no notable adverse in-life events were observed when SAF312 was administered up to a dose concentration of 25 mg/ml (2.5%) four times daily for 13 weeks.

Based on these data, the Phase 2 study includes dosing of SAF312 at concentrations of 5 mg/ml (0.5%, lowest feasible dose) and 15 mg/ml (1.5%, highest feasible dose) to ensure evaluation of the full range of possible concentrations, and evaluation of concentrations that have potential to reveal a dose response based on differentiated tissue exposure. With target tissue exposure concentrations remaining well above the estimated IC₉₀ for at least 12 hours, b.i.d. dosing has been selected as the dosing frequency.

Twelve weeks of exposure will allow for proper assessment of: 1) the efficacy of treatment response, 2) the safety of prolonged TRPV1 inhibition in the eye, and 3) the sustainability of the effect of the treatment (eg, no loss of effect over time). Both eyes will be treated with the IMP. Because it is difficult for subjects to clearly delineate pain from one eye or the other, treating both eyes will avoid confounding the data with pain that may not be addressed in the eye that does not receive treatment. There have been no safety concerns identified with the use of SAF312 eye drops, and the systemic exposure via topical ocular administration is very low, therefore dosing both eyes is not expected to pose additional safety risks to the subject.

Because PK has already been evaluated in both the FIH and the Phase 2a PRK (PoC) studies, PK is not planned as part of this Phase 2 study in patients with CICP. Plasma samples may, however, be collected ad hoc in cases of SAEs.

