6.1.3 Treatment arms/group

At Baseline (Visit 2), all eligible subjects will be randomized (ratio 1:1:1) via Interactive Response Technology (IRT) to one of the treatment arms in the double-blinded treatment.

- SAF312 Placebo eye drops, suspension, b.i.d.
- SAF312 5 mg/ml (0.5%) eye drops, suspension, b.i.d.
- SAF312 15 mg/ml (1.5%) eye drops, suspension, b.i.d.

`

Treatment duration

6.1.4

Subjects will dose both eyes with their assigned treatment for 12 weeks (84 days).

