1.2 Study objectives and endpoints

Objective(s)		Endpoint(s)		
Primary objective(s)		En	dpoint(s) for primary objective(s)	
•	To demonstrate the efficacy of at least 1 of 2 concentrations of SAF312 (5 mg/ml or 15 mg/ml) with superiority to placebo in reducing ocular pain severity	•	Change from baseline to Week 12 in weekly mean pain severity Visual Analog Scale (VAS)	
Se	condary objective(s)	En	dpoint(s) for secondary objective(s)	
•	To evaluate additional efficacy of 2 concentrations of SAF312 vs placebo	•	Change from baseline to Day 7 and Day 14 using the pain severity VAS	
		•	Change from baseline to Week 12 in pain frequency VAS	
		•	Change from Baseline to Week 12 in Ocular Pain Assessment Scale (OPAS) sub-scale Quality of Life	
•	To demonstrate SAF312 does not induce negative effects to the ocular surface after prolonged TRPV1 inhibition	•	Change from baseline to Week 12 in ocular surface parameters (e.g. corneal and conjunctival staining score, Schirmer score, conjunctival redness score)	

Table 1-1Objectives and related endpoints

Novartis SAP	For busine	For business use only		Page 9 of 33 CSAF312B12201	
Objective(s)		En	dpoint(s)		
• To evaluate the safety of SAF312 (0.5 and 1.5%)	of 2 concentrations of	٠	Comparison of adverse ev between active and place	vents rates	
Exploratory objective(s)		En	dpoint(s) for exploratory	objective(s)	
 To monitor a subject's ta artificial tear/gel/lubrication 	ehavior regarding nt use	•	Frequency of artificial tear over the 12-week treatme	/gel/lubricant use nt period	
• To monitor a subject's to rescue medication use	ehavior regarding	•	Frequency of rescue med the 12-week treatment pe	ication use over riod	
 To evaluate corneal ner morphology 	ve density and	•	Change from Baseline to corneal nerve fiber length Presence of microneurom	Week-12 in total as	

2 Statistical methods

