2.7 Analysis of secondary efficacy objective(s)

2.7.1 Secondary endpoints

For secondary endpoints:

- Change from baseline in pain severity Visual Analog Scale (VAS) at Day 7 and Day 14
- Change from baseline to Week 12 in pain frequency VAS
- Change from baseline in OPAS subscale Quality of Life at Week 12
- Change from baseline to Week 12 in ocular surface parameters (corneal staining score, conjunctival staining score, Schirmer score, conjunctival redness score)

Novartis	For business use only	Page 19 of 33
SAP		CSAF312B12201

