2.7.2 Statistical hypothesis, model, and method of analysis

No statistical hypothesis test will be performed on the secondary endpoints. Summary statistics (mean, median, 25th percentile, 75th percentile, standard deviation, minimum and maximum, the number of non-missing observations, and 95% confidence interval) by treatment arm will be provided.95% confidence interval will be provided for the difference between the SAF312 arm vs. placebo for pain severity VAS, pain frequency VAS, OPAS subscale Quality of Life and ocular surface parameters.

Where laterality applies, each eye will be summarized separately.

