2.8 Safety analyses

For all safety analyses, the SAF will be used. All listings and tables will be presented by treatment group.

Adverse Events will be reported at subject level and other safety endpoints will be reported at eye level (Left and Right) where appropriate.

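### Both eyes get the same drug, but the SAP appears to give the ocular-surface comparisons with placebo separately for left and right eyes, with no subject-level estimate

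*SAP*

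**What the plan says.** The subject is the unit of randomisation (Protocol 6.3.2), and Protocol 4.2 states: "Both eyes will be treated with the IMP". The protocol's treatment-duration paragraph (6.1.4) repeats that both eyes are dosed for the full 12 weeks.

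The objective at issue, in SAP 1.2, is: "To demonstrate SAF312 does not induce negative effects to the ocular surface after prolonged TRPV1 inhibition". It names no eye. Its endpoints are changes to Week 12 in corneal staining, conjunctival staining, Schirmer score and conjunctival redness (SAP 2.7.1).

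SAP 2.7.2 rules out hypothesis tests for secondary endpoints. It provides a 95% interval for SAF312 "vs. placebo for pain severity VAS, pain frequency VAS, OPAS subscale Quality of Life and ocular surface parameters". The next sentence is the by-eye rule: "Where laterality applies, each eye will be summarized separately".

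For safety, SAP 2.8 says: "Adverse Events will be reported at subject level and other safety endpoints will be reported at eye level (Left and Right) where appropriate".

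Neither document defines a two-eye mean, a worse eye or a model for paired eyes. Protocol 8.4.4 mentions a study eye for the slit lamp but never defines one. The averaging rule in SAP 2.1.1.5 handles repeat records within a visit window and says nothing about combining eyes.

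**The concern.** Drug, concentration and schedule are the same in both eyes, so the left/right label carries no treatment contrast. Splitting by it gives two correlated answers to one subject-level question, for each parameter and each concentration. Each answer uses one of the two measurements available per subject.

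What is at stake is the clarity and precision of the answer on ocular-surface harm. If the left interval and the right interval point different ways, the plan does not say how they combine. A combining rule chosen after unblinding would be post hoc.

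**Working it through.** **The plan's own figure.** The only power figure is for the primary pain VAS: about 83% with 50 per arm, a 15 mm difference and SD 23 mm (Protocol 12.8.1, SAP section 3). A two-sample t calculation at two-sided 0.05/2 = 0.025 gives 83.6%, which agrees. Pain VAS is one value per subject, so nothing below changes this figure.

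**Inputs.**
- n = 50 per arm, the planned number.
- Between-eye correlation r of the change scores: not in the documents. Assumed 0.5 to 0.9.
- SD of each ocular surface score: not in the documents. Results are therefore in units of the single-eye SD.
- Equal variance in the two eyes: assumed, and plausible because both eyes are treated alike.

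**Formulas.**
- Variance of the two-eye mean = single-eye variance × (1 + r)/2.
- 95% half-width for SAF312 minus placebo, one eye: 1.96 × √(2/50) = 1.96 × 0.2 = 0.392 SD.
- Same, two-eye mean: 0.392 × √((1 + r)/2).
- Subjects per arm that a single-eye analysis would need for the same precision: 50 × 2/(1 + r).

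**Results.**

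| r (assumed) | √((1+r)/2) | Half-width, two-eye mean (SD) | Narrower than one eye by | Equivalent n per arm |
|---|---|---|---|---|
| 0.5 | 0.866 | 0.339 | 13.4% | 66.7 |
| 0.7 | 0.922 | 0.361 | 7.8% | 58.8 |
| 0.8 | 0.949 | 0.372 | 5.1% | 55.6 |
| 0.9 | 0.975 | 0.382 | 2.5% | 52.6 |
| 1.0 | 1.000 | 0.392 | 0% | 50.0 |

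The percentage narrowing depends only on r, so fewer evaluable subjects would not change it.

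**Can a reader rebuild the averaged interval from the planned tables?** The standard error of the two-eye difference is ½ × √(SE_L² + SE_R² + 2r × SE_L × SE_R). Left and right tables give SE_L and SE_R but not r. For r between 0 and 1 the half-width is only known to lie between 0.392 × 0.707 = 0.277 SD and 0.392 SD. The interval cannot be recovered.

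**The case against.** **No decision rests on these intervals.** The SAP has no key secondary objective (2.6) and does not test secondary endpoints. This stands, and it limits the point to clarity and precision. No margin is stated for the harm objective either, and a narrower interval does not supply one.

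**The by-eye interval is an inference.** SAP 2.7.2 says each eye is summarised separately. It does not say in terms that the between-arm interval is computed per eye. That is the natural reading, but it remains a reading. Protocol 12.5 does not list the ocular surface parameters for between-arm intervals at all; the SAP adds them, although SAP section 4 records no change to protocol analyses.

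**The gain may be small.** At r = 0.9 it is 2.5%. This stands for precision. The lack of a defined subject-level answer does not depend on r.

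**By-eye display suits a harm question.** A mean can dilute harm in one eye, and eyes may differ within a subject, since surgery dates can differ and enhancement may be in one eye only (Protocol section 3). This is a good reason to keep by-eye tables and add a worse-eye one. It does not favour left/right as the main split, because those labels do not track surgical history.

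**Stronger readings to avoid.**
- A reader might infer that half the information is lost. It is not: for r from 0.5 to 0.9, averaging is worth about 5% to 33% more subjects (52.6/50 to 66.7/50).
- A reader might count intervals and infer a false-positive problem. The endpoints are untested. The count is not fixed either: with a single redness score it is 4 × 2 eyes × 2 concentrations = 16. Protocol 8.5.1.2 grades temporal and nasal regions without a total, and keeping them apart gives 3 × 2 × 2 + 2 × 2 × 2 = 20.
- A reader might extend the precision argument to visual acuity and IOP. SAP 2.8.4 plans by-arm summaries for these and no between-arm interval, so the argument does not reach them. Slit lamp, fundus and endothelial results are only listed, and adverse events are already per subject.

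**Conclusion.** The point holds as a low-cost improvement to the SAP. As most naturally read, the ocular-surface objective gets separate left-eye and right-eye comparisons with placebo and no subject-level estimate, although treatment is identical in both eyes. An interval from the two-eye mean would be about 13% narrower at r = 0.5, falling to 2.5% at r = 0.9, and readers cannot derive it from the planned output. The size rests on an assumed r and on equal variances. The direction holds for any r below 1 given equal variances. The primary analysis, type I error and sample size are untouched.

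**What to change.** In SAP 2.7.2, for corneal staining, conjunctival staining, Schirmer and redness:

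- Make the subject-level mean of the two eyes the main summary and the basis of the 95% interval for each SAF312 concentration minus placebo.
- For redness, apply this to each region, or define a total first.
- State what is done when only one eye has a value.
- Keep left/right tables as supporting output, and add a worse-eye summary with the direction of worsening defined for each parameter, so that one-sided harm is not averaged away.

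Leave the by-eye descriptive summaries of visual acuity and IOP in SAP 2.8.4 as they are.

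The cost is a few lines of SAP text, a two-eye mean and a worse-eye value per parameter, and the matching tables. No new data are needed, and the change should be made before unblinding.

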2.7.3 Handling of missing values/censoring/discontinuations

All observed data will be used for analysis and missing data will not be imputed.

2.8 Safety analyses

For all safety analyses, the SAF will be used. All listings and tables will be presented by treatment group.

Adverse Events will be reported at subject level and other safety endpoints will be reported at eye level (Left and Right) where appropriate.

2.8.1 Adverse events (AEs)

Summary tables for AEs will summarize for pre-treatment AEs and treatment emergent AEs (TEAEs) separately:

- Pre-treatment AEs are adverse events started between ICF signature and prior to the first administration of study treatment.
- TEAEs are adverse events started after the first administration of study treatment or events present prior to start of the treatment but increased in severity based on preferred term.

The number and percentage of subjects with AEs will be summarized for ocular and non-ocular respectively, by treatment, in the following ways:

- Primary system organ class and preferred term.
- Primary system organ class, preferred term and maximum severity.
- Standardized MedDRA Query (SMQ) and preferred term.

Separate summaries for TEAEs will be provided for study medication related AEs, death, serious adverse events (SAE), other significant AEs leading to discontinuation.

A subject with multiple adverse events within a primary system organ class is only counted once towards the total of the primary system organ class. All of these analyses will be based on the most updated MedDRA version available prior to the database lock.

All adverse events reporting will be included in the subject listings respectively.

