10.1.3 SAE reporting

To ensure subject safety, every SAE, regardless of causality, occurring after the subject has provided informed consent and until 30 days after the last study visit must be reported to Novartis safety immediately, without undue delay, under no circumstances later than within 24 hours of learning of its occurrence. Detailed instructions regarding the submission process and requirements are to be found in the investigator folder provided to each site. Information about all SAEs is collected and recorded on the eSAE with paper back. Serious Adverse Event Report Form; all applicable sections of the form must be completed in order to provide a clinically thorough report.

All follow-up information for the SAE including information on complications, progression of the initial SAE and recurrent episodes must be reported as follow-up to the original episode within 24 hours of the investigator receiving the follow-up information. An SAE occurring at a different time interval or otherwise considered completely unrelated to a previously reported one must be reported separately as a new event.

If the SAE is not previously documented in the Investigator's Brochure or Package Insert (new occurrence) and is thought to be related to the study treatment, a CMO & PS Department associate may urgently require further information from the investigator for health authority reporting. Novartis may need to issue an Investigator Notification to inform all investigators involved in any study with the same study treatment that this SAE has been reported.

Suspected Unexpected Serious Adverse Reactions (SUSARs) will be collected and reported to the competent authorities and relevant ethics committees in accordance with European Union (EU) Guidance 2011/C 172/01 or as per national regulatory requirements in participating countries.

Any SAEs experienced after the 30 day period after the last study visit should only be reported to Novartis Safety if the investigator suspects a causal relationship to study treatment.

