12.5.1 Safety endpoints

For all safety analyses, the safety set will be used. The safety assessments are adverse events (ocular and non-ocular), slit lamp biomicroscopy, IOP, visual acuity, ophthalmoscopy, and corneal endothelial cells evaluations. All listings and tables will be presented by treatment group.

Safety summaries (tables, figures) include only data from the on-treatment period with the exception of baseline data which will also be summarized where appropriate (e.g. change from baseline summaries). In addition, a separate summary for death including on treatment and post treatment deaths will be provided. In particular, summary tables for adverse events (AEs) will summarize only on-treatment events, with a start date during the on-treatment period (treatment-emergent AEs).

The on-treatment period starts from the date of the first administration of study treatment to 4 days after the date of the last administration of study treatment.

The safety analysis will consist of descriptive summaries. Continuous variables will be presented with n, mean, SD, median, minimum and maximum. Categorical data will be displayed with frequency and percentage.

Adverse events

All information obtained on adverse events will be displayed by treatment group and subject.

The number (and percentage) of subjects with treatment emergent adverse events (events started after the first dose of study medication or events present prior to start of double-blind treatment but increased in severity based on preferred term) will be summarized in the following ways:

- by treatment, primary system organ class and preferred term.
- by treatment, primary system organ class, preferred term and maximum severity.
- by treatment, Standardized MedDRA Query (SMQ) and preferred term.

Ocular and non-ocular adverse events will be summarized separately. Separate summaries will be provided for study treatment related adverse events, death, SAE, other significant adverse events leading to discontinuation.

Subject listings of all adverse events will be provided. Deaths and other serious or clinically significant non-fatal adverse events will be listed separately. A subject with multiple adverse events within a primary system organ class is only counted once towards the total of the primary system organ class.

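### SAP 2.8.1 leaves out the protocol's cut-off of 4 days after last dose for tabulated adverse events, and SAP section 4 declares no change

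*SAP*

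**What the plan says.** Protocol 12.5.1 states the restriction directly: "summary tables for adverse events (AEs) will summarize only on-treatment events, with a start date during the on-treatment period". It labels these events treatment-emergent and sets the limits of the period, which "starts from the date of the first administration of study treatment to 4 days after the date of the last administration". It adds a separate death summary that covers deaths both during and after treatment.

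Further down, the same section describes treatment-emergent events in a parenthesis as "events started after the first dose of study medication or events present prior to start of double-blind treatment but increased in severity based on preferred". That wording has no end date.

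SAP 2.8.1 divides adverse events into two classes only, pre-treatment and treatment-emergent. The second is defined so: "TEAEs are adverse events started after the first administration of study treatment"; pre-existing conditions that later worsen are added. No end date follows and there is no post-treatment class. SAP 2.8.1.2 builds the public disclosure tables on the same definition. SAP section 4, which is the place for changes to protocol-specified analyses, reports none.

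On collection, Protocol 10.1.1 continues adverse event monitoring to the end-of-study visit. Protocol section 8 lets the end-of-study contact be later than EOT + 4 days but not earlier. Protocol 9.1.1 requires adverse events to be collected after study treatment is discontinued. Protocol 10.1.3 requires reporting of serious events "occurring after the subject has provided informed consent and until 30 days after the last study visit".

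**The concern.** The protocol bounds the tables and the SAP does not, so the two documents can put the same event in different places. Because the SAP has no post-treatment class, any event collected after the protocol's window closes falls into the treatment-emergent class by default. Comparison of adverse event rates between active and placebo is a secondary endpoint (Protocol Table 2-1, SAP Table 1-1), and the disclosure tables depend on the same definition. A programmer working from the SAP would apply no upper date limit, and a reader of the report would be told that nothing had changed from the protocol.

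**Working it through.** **Is the bound restored elsewhere in the SAP?**

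- SAP 2.1.1.4 uses the term on-treatment for other measurements, but the SAP does not define it.
- SAP 2.4.1 defines exposure as last dose date − first dose date + 4 + 1. The 4-day tail is therefore used for exposure but not for adverse events.
- SAP 5.1.1.1 caps imputed adverse event end dates. It does not limit when an event may start.

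The bound is not restored.

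**How many days separate the two rules?** Neither document gives a figure to reproduce, so this is day arithmetic.

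Inputs: first dose on Day 1; treatment for 84 days (Protocol 6.1.4); window closing at last dose + 4 (Protocol 12.5.1); end-of-study contact at EOT + 4 (Protocol Table 8-1), so 84 + 4 = Day 88 as planned; serious event reporting to 30 days after the last visit (Protocol 10.1.3), so 88 + 30 = Day 118 if that contact counts as the last visit.

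Formulas:

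- Window closes = last dose day + 4
- Extra days, all adverse events = 88 − (last dose day + 4)
- Extra days, serious events = 118 − (last dose day + 4)
- SAP exposure = last dose day − 1 + 4 + 1

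Assumption: the subject is followed to the planned Day 88 whatever the stopping day.

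| Last dose day | Window closes | Extra days, all AEs | Extra days, SAEs | SAP exposure (days) |
|---|---|---|---|---|
| 84 | 88 | 0 | 30 | 88 |
| 56 | 60 | 28 | 58 | 60 |
| 42 | 46 | 42 | 72 | 46 |
| 28 | 32 | 56 | 86 | 32 |
| 14 | 18 | 70 | 100 | 18 |
| 1 | 5 | 83 | 113 | 5 |

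**How firm is the Day 88 assumption?** It is not fixed by the documents. Protocol 9.1.1 has subjects who stop treatment return for the end-of-treatment and follow-up visits, and otherwise prefers telephone contact on the visit schedule. If the end-of-treatment visit takes place on the day of stopping and the follow-up contact 4 days later, a subject stopping on Day 42 is last contacted on Day 46, and the excess is 46 − 46 = 0. The range for routine adverse events is therefore 0 to about 83 days. For a completer, each day by which the end-of-study contact is late adds one day.

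**Do late serious events reach the tables?** Protocol 10.1.3 governs reporting to the sponsor's safety group. Neither document says whether a serious event after the end-of-study contact enters the data behind the SAP tables. The serious-event column holds only if it does.

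**The case against.** The best defence is that the SAP invented nothing. Its definition closely follows the parenthesis in Protocol 12.5.1, and its introduction says that it implements the protocol's planned analysis. With the 4-day tail present in SAP 2.4.1, a dropped sentence is likelier than a deliberate change. That stands as an account of the cause. It does not remove the conflict. The protocol states the restriction explicitly, and its separate provision for post-treatment deaths would hardly be needed if the event tables were already open-ended.

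Several stronger readings are tempting, and the documents do not support them:

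- *Off-drug events are being called on-treatment.* The SAP calls them treatment-emergent. It is the protocol that equates the two terms.
- *The active-versus-placebo comparison is biased.* If stopping differs by arm, truncation also gives unequal observation time. Suppose 20% of one arm stop on Day 42 and nobody stops in the other. Under the protocol rule the mean windows are 0.2 × 46 + 0.8 × 88 = 79.6 days and 88 days. Under the SAP rule with follow-up to Day 88, both are 88. Conformity with the protocol supports the fix; an argument from distortion does not.
- *A share of off-drug person-time measures the effect.* With 10, 15 or 20% stopping on Day 42 (assumed), p × 42/88 gives 4.8, 7.2 or 9.5%. But the SAP tables count subjects, and such a share does not show how many would change category.
- *Completers carry a 34-day tail of serious events.* Four of those days (30 + 4) already lie inside the protocol's window. The excess is 30 days with an on-time contact.

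**Conclusion.** The discrepancy is real and undeclared. Followed literally, SAP 2.8.1 would place in the treatment-emergent tables events that the protocol's main rule keeps out. The exposed cases are subjects who stop treatment early and are still followed, completers with a late end-of-study contact, and late serious events if they enter the clinical database. For completers contacted on time, routine non-serious events are treated identically under both rules.

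The excess counting time for early stoppers is 0 to about 83 days for routine events. The upper end requires stopping after the first dose and follow-up to Day 88. The documents give no adverse event or discontinuation rates, so the number of reclassified subjects cannot be derived. The safety analysis is descriptive and the primary efficacy analysis is untouched. The point should be settled before database lock because it governs a secondary endpoint and the disclosure tables and is cheap to settle. Confidence is high on the mismatch in the text; its effect on the tables is unknown.

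**What to change.** In SAP 2.8.1, extend the treatment-emergent definition so that onset or worsening must fall no later than 4 days after last dose, and let 2.8.1.2 inherit it. Add a post-treatment category and report later events there. Keep the protocol's separate death summary covering both on-treatment and post-treatment deaths. SAP 2.8.1 now summarizes deaths within the treatment-emergent tables, and SAP 2.8.2 provides only a listing, so bounding the definition alone would remove post-treatment deaths from that summary and create a new departure. It would also help to align the open-ended parenthesis in Protocol 12.5.1 with the restriction above it.

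If the sponsor wants the wider window, it should say so and justify it in SAP section 4.

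The cost is one SAP sentence, one date filter and a post-treatment display. The downside is that events after the window leave the main table, and observation time per subject becomes shorter for early stoppers. Reading the table beside SAP 2.4.1 exposure, which uses the same tail, makes that visible.
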